## **V. STUDY PROCEDURES**

We will recruit 132 participants with major lower unilateral limb amputation and phantom limb pain in the chronic phase.

The patients will be assigned to one of four groups: the first will receive active tDCS and active MT; the second will receive sham tDCS and active MT; the third will receive active tDCS and sham MT; and the fourth will receive both sham tDCS and sham MT. Subjects and outcome evaluators will be blinded to the intervention assigned. The study will be done for a total of 13 weeks. The study procedures will be done in the same way in both study centers. Data collection will be performed according to the IRB approved protocol by trained and capable research staff. The Neuromodulation Center (Spaulding Rehabilitation Hospital) will be responsible for providing training and responsible for monitoring of the study, including maintaining regular contact with the University of Sao Paulo site through telephone contact. This phone contact will be logged and stored at the Regulatory binder. The data will be collected by staff members (PI, co-investigators and study staff) familiar with the protocol and the tDCS and TMS technology. The care, safety, and comfort of the subjects will be under the supervision of a physician and therapist at each trial site. The local IRB at each respective institution will be responsible for overseeing the conduct of the study trial locally. Both IRB institutions approved the research protocol. Unidentifiable data from the local institution in Brazil will be shared with the main site (Boston) via IRB approved data base RedCap. There will be no sharing of PHI between the sites.

The subjects randomized to receive sham tDCS and/or sham MT will have the opportunity to enroll into an open label portion of the study at the conclusion of their participation in the randomized portion of the trial, including 10 sessions of tDCS combined with MT and additional questionnaire data.

## **Study Outline**

### *Pre-screening Procedures:*

During the pre-screening process, the subject will contact a co-investigator usually via a phone call. During this call, the co-investigator will discuss in greater depth the details of the study, explain the study procedures and encourage the subject to ask questions. In the privacy of the laboratory, the co-investigator will ask the subject questions from the following:

- 1) Phone screening questionnaire

Once this information is collected, the co-investigator will consult with the PI regarding the eligibility of the subject, who will then give approval for the subject to come to our laboratory for the screening procedure.

### **Visit 1**

Screening Visit – (Approximate Time: 1 hour)

### *Screening Procedures:*

At Screening the PI and/or a co-investigator will conduct, once more a review of inclusion/exclusion criteria to determine the subject's eligibility for enrollment. Study procedures will be reviewed with the subject, and documentation of informed consent will be obtained.

At Screening the following procedures will be completed:

- Discuss study-specific procedures with the subject.

- Review inclusion and exclusion criteria.
- Obtain a signed and dated consent form.
- Conduct a Demographics Survey, Brief Medical History and Beck depression inventory.
- fMRI screening questionnaire\*.
- Urine pregnancy exam (if applicable).

\* If the subject is not eligible for an fMRI at the time of the study we will not perform this assessment as fMRI is not required for study eligibility and it is only used as a secondary outcome.

Randomization:

Once eligibility and consent have been approved and completed, randomization will occur using the randomized list generated by an automatic web-base randomization program ([www.randomization.com](http://www.randomization.com)). Subjects will be randomly assigned to one of the four groups in a 1:1:1:1 allocation ratio. We will use stratified randomization methods with random block sizes of blocks of 4 and 8. Patients will be stratified based on their baseline pain levels (two strata: less or equal of average 6 in VAS or more than 6 in VAS) and by study center (IMREA or SRH-Neuromodulation Lab). Randomization order will be kept in sealed envelopes; therefore subjects will get their assignment according to the order of entrance in the study (for instance, subject 1 will be assigned the first envelope that will contain his/her assignment according to this block randomization list).

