## II. SPECIFIC AIMS

The specific aims of this experiment are as follows:

[figure not shown]
- **Aim 1: To evaluate the efficacy of tDCS and mirror therapy (MT) as rehabilitative tools for the management of chronic PLP patients.**

We will explore the aim 1 in a randomized factorial controlled trial in which patients will be assigned to one of four groups: active tDCS and active MT; sham tDCS and active MT; active tDCS and sham MT (which consists of using a covered mirror for the therapy); and both sham tDCS and sham MT (covered mirror).

The primary end point will be severity of pain measured by changes in PLP as indexed by a Visual Analog Scale (VAS). The study will require a total of 13 weeks to be completed. The first week, each patient will give daily reports of their pain using a VAS, accounting for their PLP experience in the past 24hs. This initial baseline week will be followed by 4 weeks of treatment (tDCS and/or MT) and a final 8-week follow-up period without any treatment to examine long-lasting effects of each therapy. *Our hypothesis is that the combined intervention (tDCS and MT) will result in a greater pain reduction as compared with any therapy alone and no therapy.*

- **Aim 2: To examine the mechanisms underlying PLP using two neurophysiological techniques.**

For each of the four groups described in aim 1, we will determine the neural correlates of the effect. We will use single-pulse and paired-pulse transcranial magnetic stimulation (TMS) to assess cortical mapping and cortical excitability changes associated with cortical reorganization. We will also use functional magnetic resonance imaging (fMRI) to assess brain changes, including the quantification of maladaptive cortical reorganization. Using fMRI, we will determine the changes in Blood-Oxygen-Level dependent activation between the sensory-motor cortex of the affected and unaffected side after the treatment. We will compare these neurophysiological parameters before and after treatment in each of the four groups. *Our hypothesis is that the combined group (tDCS and mirror therapy) will have a greater activation than any therapy alone and also than the no therapy group (sham tDCS and covered mirror). This effect will also be correlated with pain reduction.*

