**Inclusion Criteria:**

1. Able to provide informed consent to participate in the study.
2. Subject is older than 18 years.
3. Unilateral lower limb amputation.
4. 3 months of phantom limb pain (experienced regularly for at least once a week) after the amputated limb has completely healed.\*
5. Average pain of at least 4 on a numeric rating scale in the previous week (NRS; ranging from 0 to 10).
6. If the subject is taking any medications, dosages must be stable for at least 2 weeks prior to the enrollment of the study.

[figure not shown]
\*The healing status of the limb will need to be confirmed by the subject's physician or by the physician of the protocol [name] (Co-Investigator).

[figure not shown]

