**Visit 2**

Baseline Visit – (Approximate Time: 2 hours)

*This visit might be completed on the same day as the screening visit if time allows and the subject agrees.*

Baseline assessments:

- Visual Analogue Scale (VAS) for Pain
- Visual Analogue Scale (VAS) for Stump pain
- Visual Analog Scale (VAS) for Phantom Limb Sensation
- Visual Analog Scale (VAS) for Phantom Limb Telescoping
- Adapted Groningen Questionnaire After Arm Amputation
- Pain and Medication use diary\*
- Beck Anxiety Inventory
- Mini Mental State examination (MMSE)
- Stroop Test
- Health Survey SF-36
- Single and paired pulse TMS
- Side Effects Questionnaire for TMS

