**Visit 3**

fMRI Evaluation – (Approximate Time: 1 hour)

*\*\*Visits 1-3 may be completed on the same day or broken up into two or three separate visits as the subject prefers*

**Visit 4 – 12** (Approx Time: 45 minutes)

Intervention visits: tDCS + Mirror Therapy

*This visit will be scheduled within 1 week after the baseline measurements are done.*

In the first 2 weeks subjects will receive tDCS (\*sham or active) and mirror therapy (sham or active). There will be 10 stimulation visits to be completed in these 2 weeks (ideally Monday to Friday, 5 days each week). The subject will receive 20 minutes either of active or sham tDCS per day and 15 min of active or sham mirror therapy sessions. The subjects will receive the intervention according to the prior randomized group.

Before stimulation, the subject will complete the following assessments:

- VAS Phantom Limb Pain
- VAS for Stump pain
- VAS for Phantom Limb Sensation
- VAS for Phantom Limb Telescoping

After each session, subjects will complete the following assessments:

- Side Effects Questionnaire for tDCS
- VAS Phantom Limb Pain
- VAS for Stump pain
- VAS for Phantom Limb Sensation
- VAS for Phantom Limb Telescoping

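### Does the plan randomise patients before the pain score that sets their stratum exists?

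*Combined protocol and SAP*

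**What the plan says.** The Randomization paragraph sits in the Visit 1 section, under Screening Procedures. It opens: "Once eligibility and consent have been approved and completed, randomization will occur using the randomized list". It then sets four arms at 1:1:1:1, with stratified randomisation in random blocks of 4 and 8. "Patients will be stratified based on their baseline pain levels", the two levels being an average VAS of 6 or less and above 6; the second factor is study centre, with two levels. Assignments are kept in sealed envelopes and used in order of entry, with the illustration that "subject 1 will be assigned the first envelope that will contain his/her assignment according to this block randomization list".

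Pain is measured in several places:

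- **Inclusion Criteria:** "Average pain of at least 4 on a numeric rating scale in the previous week".
- **Visit 2:** the baseline list begins with "Visual Analogue Scale (VAS) for Pain".
- **Specific Aims, Aim 1:** "The first week, each patient will give daily reports of their pain using a VAS", each report covering the past 24 hours, before the four treatment weeks.
- **Description of Assessments:** the pain diary records the intensity of the strongest episode.

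On the start of treatment, the Visit 4–12 text says: "This visit will be scheduled within 1 week after the baseline measurements are done". It adds: "The subjects will receive the intervention according to the prior randomized group". Visits 1 to 3 may be held on one day or spread over two or three.

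**The concern.** Three things look unsettled.

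1. **Allocation point.** Randomisation is described under a visit whose procedure list has no pain scale, yet it depends on a VAS average collected later. If an envelope really were opened at screening, the stratum would be unknown or would have to be taken from something else. A patient lost before the first VAS would also have been randomised with no value for the intention-to-treat rule, which holds participants at their last measured point.
2. **Stratifying measure.** An average VAS is named, but neither its window nor its source. The eligibility NRS, the single Visit 2 rating, the daily past-24-hour VAS and the diary's strongest-episode score are different quantities. If the two centres chose differently, the same patient could fall in different strata.
3. **Envelope series.** Two centres by two pain levels need four series. The worked example speaks of subject 1 and the first envelope, as if there were one. A single sequence that ignored strata would not deliver the promised balance on baseline pain, which is the baseline of the primary outcome.

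**Working it through.** **Timing.** Setting the sections side by side:

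| Section | What it fixes about timing |
|---|---|
| Visit 1, Randomization | Not before eligibility and consent are complete; no day named |
| Visit 2 | Baseline VAS; may be the same day as screening |
| Visit 3 (note) | Visits 1 to 3 on one day or on separate days |
| Visit 4–12 | Group already assigned; first session within a week of baseline |
| Specific Aims | Baseline week of daily VAS precedes treatment |

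The first row gives only an earliest point and the fourth only a latest one. The order consent, baseline VAS, envelope, Visit 4 satisfies all five rows. The literal reading, with an envelope at screening before any VAS, cannot be carried out as stratified randomisation, because the person choosing the envelope would not know the stratum. Of the two readings, only one can be operated.

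**Measure.** The text specifies a VAS, which rules out the eligibility NRS. It specifies an average, which a single Visit 2 rating fits poorly. The baseline week of daily VAS reports is the natural source of an average. The diary's strongest-episode item is the one real rival, and it is a maximum rather than an average level.

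**Size if a different measure were used.** Inputs: mean 6.4 and SD 1.6, the control figures in Sample size calculation, borrowed here as baseline values; cut at 6; both measures taken as bivariate normal with the same mean and SD. The correlation ρ is an assumption.

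- z = (6 − 6.4)/1.6 = −0.25, and Φ(z) = 0.401.
- Proportion in different strata = 2 × [Φ(z) − Φ₂(z, z; ρ)].

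| ρ | Φ₂ | Proportion | Of 132 |
|---|---|---|---|
| 0.9 | 0.332 | 0.139 | 18 |
| 0.8 | 0.302 | 0.198 | 26 |
| 0.7 | 0.279 | 0.245 | 32 |
| 0.6 | 0.259 | 0.285 | 38 |

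These are counts of patients labelled differently by two scales. Any measure taken before allocation gives a valid stratifier, so none of these patients contributes bias.

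**Envelopes.** 2 centres × 2 pain levels = 4 strata. The paragraph specifies stratified randomisation, which implies a list for each stratum. The subject 1 sentence is introduced as an instance, and it is equally true of the first patient in each of the four series. It omits the strata without contradicting them.

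**Sample size.** The plan's figure is unaffected. With SD = √[(1.5² + 1.6²)/2] = 1.551 and difference 6.4 − 5.2 = 1.2, the normal-approximation formula at two-sided 0.05 and 80% power gives 27 per group, or 108. Then 27 × 1.2 = 32.4, rounded up to 33 per group, gives 132. Neither figure depends on when or how the stratum is set.

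**The case for a change.** The best case for a change is that the envelope sentence is the only operating instruction site staff have, and it never mentions strata. The trial runs at two centres in different countries, overseen by telephone. Baseline pain is also listed as a covariate in the pain models under Statistical Analysis, so its definition matters beyond allocation. There is real friction, too, between a full baseline week and a first session that may fall any time within a week of the baseline measurements: a patient treated early would not have seven daily reports. A few sentences would remove all this at almost no cost.

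Much of that stands as a description. No surviving section names the averaging window or the allocation step, and the baseline-week timing is not tied to Visit 4. What does not stand is the harm. Study Procedures requires both centres to work in the same way and makes one of them responsible for training and monitoring, which makes divergent classification less likely. The main model takes baseline as a level of time, and the further pain models list site and baseline pain as covariates, which limits the cost of imperfect strata. The risk of envelopes being drawn from one sequence depends on a reading that the word stratified already argues against. The evidence is also incomplete: the body of Table 1 and Figure 1 are not shown, the footnote to the Visit 2 diary item does not survive, and the phone screening items are not listed. Any of these could contain the missing detail.

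**Conclusion.** This is missing operational detail that the people running the trial fill sensibly. A workable sequence agrees with every section, the stratifier is best read as the mean of the baseline-week VAS reports, and stratified randomisation implies a separate envelope series for each of the four centre-by-pain strata. On that reading no patient is allocated without a VAS value. Even on a less favourable choice of measure, about 18 to 38 of 132 patients would be labelled differently. That range rests on figures borrowed from a spinal cord injury study, equal distributions for the two measures and assumed correlations of 0.9 to 0.6, and it costs neither validity nor type I error. The sample size of 132 stands. The allocation step and the averaging window can be recorded in the site randomisation instructions, so no change to the plan is needed.

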**Visit 2**

Baseline Visit – (Approximate Time: 2 hours)

*This visit might be completed on the same day as the screening visit if time allows and the subject agrees.*

Baseline assessments:

- Visual Analogue Scale (VAS) for Pain
- Visual Analogue Scale (VAS) for Stump pain
- Visual Analog Scale (VAS) for Phantom Limb Sensation
- Visual Analog Scale (VAS) for Phantom Limb Telescoping
- Adapted Groningen Questionnaire After Arm Amputation
- Pain and Medication use diary\*
- Beck Anxiety Inventory
- Mini Mental State examination (MMSE)
- Stroop Test
- Health Survey SF-36
- Single and paired pulse TMS
- Side Effects Questionnaire for TMS

**Visit 3**

fMRI Evaluation – (Approximate Time: 1 hour)

*\*\*Visits 1-3 may be completed on the same day or broken up into two or three separate visits as the subject prefers*

**Visit 4 – 12** (Approx Time: 45 minutes)

Intervention visits: tDCS + Mirror Therapy

*This visit will be scheduled within 1 week after the baseline measurements are done.*

In the first 2 weeks subjects will receive tDCS (\*sham or active) and mirror therapy (sham or active). There will be 10 stimulation visits to be completed in these 2 weeks (ideally Monday to Friday, 5 days each week). The subject will receive 20 minutes either of active or sham tDCS per day and 15 min of active or sham mirror therapy sessions. The subjects will receive the intervention according to the prior randomized group.

Before stimulation, the subject will complete the following assessments:

- VAS Phantom Limb Pain
- VAS for Stump pain
- VAS for Phantom Limb Sensation
- VAS for Phantom Limb Telescoping

After each session, subjects will complete the following assessments:

- Side Effects Questionnaire for tDCS
- VAS Phantom Limb Pain
- VAS for Stump pain
- VAS for Phantom Limb Sensation
- VAS for Phantom Limb Telescoping

**Visit 13**

Last day of tDCS session + Mirror Therapy – (Approx Time: 2 hours)

Before stimulation, the subject will complete the following assessments:

- VAS Phantom Limb Pain
- VAS for Stump pain
- VAS for Phantom Limb Sensation
- VAS for Phantom Limb Telescoping

After each session, subjects will complete the following assessments:

- Visual Analogue Scale (VAS) for phantom limb pain
- Visual Analogue Scale (VAS) for Stump pain
- Visual Analog Scale (VAS) for Phantom Limb Sensation
- Visual Analog Scale (VAS) for Phantom Limb Telescoping
- Pain and medication use diary
- Stroop Test
- Beck Anxiety Inventory

- Beck Depression Inventory
- Side Effects Questionnaire for tDCS
- Blinding Questionnaire
- Single and paired pulse TMS
- Side Effects Questionnaire for TMS

**After the first 2 Weeks combined intervention (sham/active tDCS plus sham/real mirror therapy) at the Neuromodulation Center in front of the therapist, subjects will continue mirror therapy for 10 additional sessions over the course of ~ 2 weeks at home.**

2 weeks of home Mirror Therapy – (Approx Time: 15 min)

During this 2 week period the co-investigator will try to contact the subjects 3 times per week to assess adherence to the MT treatment and acquire pain diary and medication changes data. We are going to try maximum 2 attempts per day.

**Visit 14:**

Last day of mirror therapy - (Approx Time: 3 hours)

*This visit will be scheduled in the last MT home session and the following assessments will be performed. This visit can be divided in two days if time allows and the subject agrees.*

Subject can perform the last mirror therapy session either at home or at the Neuromodulation Center.

After the MT session, subject will complete the following assessments:

- Visual Analogue Scale (VAS) for phantom limb pain
- Visual Analogue Scale (VAS) for Stump pain
- Visual Analog Scale (VAS) for Phantom Limb Sensation
- Visual Analog Scale (VAS) for Phantom Limb Telescoping
- Pain and Medication uses diary
- Stroop Test
- Health Survey SF-36
- Patients' Global Impression of Change (PGIC) scale
- Beck Anxiety Inventory
- Beck Depression Inventory
- Single and paired pulse TMS
- Side Effects Questionnaire for TMS
- fMRI evaluation

**Visit 15:** fMRI Evaluation – (Approximate Time: 1 hour)

*\*\*Visits 14 & 15 may be completed on the same day or broken up into two separate visit as the subject prefers*

**Visit 16:**

First Follow Up Visit – (Approx Time: 1 hour)

*This visit will be scheduled ~ four weeks (+/- 5 days) after the last MT home session and the following assessments will be performed:*

- Visual Analogue Scale (VAS) for phantom limb pain
- Visual Analogue Scale (VAS) for Stump pain.
- Visual Analog Scale (VAS) for Phantom Limb Sensation
- Visual Analog Scale (VAS) for Phantom Limb Telescoping
- Beck Anxiety Inventory
- Beck Depression Inventory
- Pain Medication uses diary

*\*\*Visit 16 may be completed by terms of phone interview as the subject prefers.*

**Visit 17:**

Last Follow Up Visit - (Approx Time: 2 hours)

*This visit will be schedule ~eight weeks (+/- 5 days) after the last MT home session and the following assessments will be performed:*

[figure not shown]
- Visual Analogue Scale (VAS) for phantom limb pain
- Visual Analogue Scale (VAS) for Stump pain
- Visual Analog Scale (VAS) for Phantom Limb Sensation
- Visual Analog Scale (VAS) for Phantom Limb Telescoping
- Pain Medication uses diary.
- Stroop Test.
- Health Survey SF-36.
- Beck Anxiety Inventory
- Beck Depression Inventory
- Single and paired pulse TMS
- Side Effects Questionnaire for TMS
- Blinding questionnaire

[figure not shown]
*\*\*After visit 14 until the end of the trial participation, the co-investigator will try to contact the subjects 3 times per week to acquire pain diary and medication changes data. We are going to try maximum 2 attempts per day.*

The schedule for the subjects can be seen in table 1, which illustrates the procedures that will be performed at each visit:

**Table 1:** Visits Schedule

	Consent and Screening	Baseline	fMRI Visit	Interventions Session	fMRI Visit	Follow-Up
--	------------------------------	-----------------	-------------------	------------------------------	-------------------	------------------

observed in the mirror to their phantom limb and to keep their attention focused on the task. Instructions will be explained verbally, demonstrated by a therapist, and performed by the subject in front of the therapist during the first two weeks (the MT sessions will be scheduled back-to-back with the tDCS sessions). After this training, subjects will continue MT everyday for 2 more weeks at home. Subjects will be instructed to stop MT if it intensifies their pain, and to document if this happens

- Sham Mirror Therapy (Covered MT): Subjects will be asked to perform movements in the same way that the active group but with a covered mirror.

[figure not shown]

Figure 1: Schematic view of the experiment in time points: baseline, procedures, subjects enrolled intervention, first follow-up and second follow up.

